5.3 INTERVENTIONS

All surgeries will be performed under local anesthesia using lidocaine with epinephrine, (Xylocaine 2%®- Epinephrine 1:100,000 and 1:50,000, Dentsply Pharmaceutical, York, PA, USA).

5.3 VISIT 2 (DAY 0): BASELINE

The baseline visit should be completed within 2 weeks after visit 1 (Screening). The surgeon will extract the hopeless tooth in the following fashion. He/she will make facial and lingual intrasulcular incisions with a 15-C scalpel only at the tooth requiring extraction. A periosteal elevator will then be used at the mesial and distal aspects of the tooth to sever subcrestal periodontal attachment fibers and expand the periodontal ligament space. If needed to allow periosteal elevator insertion or facilitate removal of a root tip, a fine long diamond bur (e.g. 859-010;

Brasseler, Savannah, Ga, USA) may be used to remove bone along the side of the tooth. An elevator will be used to mobilize the tooth and then forceps will be used to deliver the tooth. Finally, the socket will be curetted to remove all granulosomatous tissue and irrigated with sterile isotonic saline solution.

1. Extraction treated with xenograft bone substitute + collagen dressing:

The debrided socket from the control group will receive Geistlich Bio-Oss® Collagen (250mg) or the necessary amount to successfully fill the extraction socket. The bone substitute material will be rehydrated with subject's blood or sterile saline solution. A collagen dressing (HeliPlug®) will be used to cover the grafted extraction socket and sutured with resorbable suturing material (5-0 Vicryl – Ethicon, Inc., Somerville, NJ) to stabilize the wound.

2. Extraction treated with xenograft bone substitute + 3D-collagen matrix:

The debrided socket from the test group will receive Geistlich Bio-Oss® Collagen (250mg) or the necessary amount to successfully fill the extraction socket. The bone substitute material will be rehydrated with subject's blood or sterile saline solution. A 3D-collagen matrix (Mucograft Seal®) will be used to cover the grafted extraction socket and sutured with non-resorbable (6-0 Prolene – Ethicon, Inc., Somerville, NJ) and resorbable (5-0 Vicryl – Ethicon, Inc., Somerville, NJ) suturing material to stabilize the collagen matrix over the extraction socket.

Subjects in both groups will be instructed to rinse twice daily with 0.12% chlorhexidine gluconate for 30 seconds and avoid brushing or touching the area of extraction for 2 weeks. After 2 weeks, subjects may resume gentle brushing of the surgical site with a soft toothbrush. Sutures will be removed 2 weeks following the surgical appointment. Subjects will return at 1 week and 4 weeks to assess plaque control and wound healing.

Subjects will be given prescriptions for postoperative medications as stated in Table 1. Patient will assume all costs for prescription medications. Temporary appliance to replace the missing tooth will not be delivered as part of the study. However, subjects can have their referring dentists fabricating and delivering a temporary appliance to replace the missing tooth during the first 6 months of the study. The temporary appliance will not be covered by the study.

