3.1 MASKING

This study will be conducted in a single masked manner such that all volumetric assessments will be performed without knowledge of the subjects' type of treatment.

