3.2 RANDOMIZATION

Qualified subjects will be assigned randomly into one of two groups: 12 subjects into the xenograft + 3D-collagen group (Test) and 12 subjects into the xenograft + collagen dressing group (Control).

The study coordinator will place 24 identically sized slips of paper, 12 reading "Test" and 12 reading "Control", into a sealed envelope. The study coordinator will select one sealed envelope for each qualified subject, and record the randomization results and staple the slip of paper into the subject study folder.

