4.4 SUBJECT IDENTIFICATION

At screening, participants will be assigned a 3-digit counter/screening number by the study center (001, 002, etc.). At treatment baseline/series, each subject will receive a unique 4-digit study number (1001, 1002, etc.) that will identify their group status in the study. Participants who do not complete the study will be replaced until 24 participants have completed the study.

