For hard tissue analysis, to test the working hypothesis of systematic differences between the treatment groups, a two-sample equal variance student t-test with a two-tailed distribution was performed comparing the two groups for each of the linear measurements as well as for the volumetric analysis. Statistical significance was defined as a p -value < 0.05 .

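### The plan does not fix whether the arm is revealed before or after the socket is grafted, and lists no record of graft used, so arm-dependent filling could bias the ridge-width comparison unseen.

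*Combined protocol and SAP*

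**What the plan says.** **Graft step.** Section 5.3 (Visit 2, Day 0) describes it once per arm, in matching words. Control: "The debrided socket from the control group will receive Geistlich Bio-Oss® Collagen (250mg) or the necessary amount to successfully fill the extraction socket". Test: "The debrided socket from the test group will receive Geistlich Bio-Oss® Collagen (250mg) or the necessary amount to successfully fill the extraction socket". The target is a filled socket; no level or check defines when it has been reached.

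**Masking.** Section 3.1 calls the trial single masked and explains that "all volumetric assessments will be performed without knowledge of the subjects' type of treatment". It says nothing about masking the surgeon.

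**Reveal of the arm.** Section 3.2 says "The study coordinator will select one sealed envelope for each qualified subject". Section 4.4 adds that at treatment baseline "each subject will receive a unique 4-digit study number (1001, 1002, etc.) that will identify their group status in the study". Neither section places the reveal before or after extraction or grafting.

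**Records and analysis.** The procedures in sections 5.3 to 5.10 do not include recording the amount of graft placed, although section 5.9 does ask for implant insertion torque. Section 7.0 plans no summary of graft use. For hard tissue, "a two-sample equal variance student t-test with a two-tailed distribution was performed", with no adjustment.

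**The concern.** The covering is the only intended difference between the arms, so the comparison is clean only if the graft beneath is placed in the same way in both. That step ends on a surgeon's judgement, and nothing in the plan prevents the surgeon from knowing the arm when making it. If filling differed by arm, for whatever reason, the difference would be built into the ridge before any image was taken. Masked reading of the scans could not remove it, and the t-test would attribute it to the covering.

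With no listed record of the amount used, neither the investigators nor a reader could check afterwards whether the arms were grafted alike. Recording alone would not be a full repair. If the arm is known before filling, the amount is a post-randomisation variable, and adjusting for it could serve only as a sensitivity analysis. Prevention at the time of reveal is the sounder course.

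**Working it through.** **1. Could the surgeon know the arm while filling?** Set the sections side by side.

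- 3.1: masking is stated for assessment only.
- 3.2: the trigger for the envelope is that the subject has qualified.
- 4.2 and 9.0: eligibility can still fail after extraction, if more than half of the buccal bone height is missing. Qualification could therefore be read as complete only after extraction, but no section ties the envelope to that check, and even this reading leaves open whether the reveal comes before or after grafting.
- 4.4: a number that identifies the arm is given at treatment baseline, again with no order relative to grafting.

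The documents are silent on the order. Knowledge of the arm during filling is permitted, not shown.

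**2. The plan's own power figure.** Inputs from section 7.0: difference 2.5 mm in horizontal width 3 mm below the crest, SD 1.6 mm, 12 per arm, 5% type I error, 10% dropout, power at least 90%. The two-sided 5% level follows the planned t-test.

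- SE = 1.6 × √(2/12) = 0.653 mm; noncentrality = 2.5/0.653 = 3.83; df = 22; power = 95.5%.
- With 10 per arm: SE = 1.6 × √(2/10) = 0.716 mm; power = 91.0%. With 9 per arm, power is 87.5%, so 10 per arm are needed.
- Dropout: 10/(1 − 0.10) = 11.1, rounded up to 12 per arm, 24 in total.

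The stated power and sample size reproduce and are not affected by this point.

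**3. What a bias would do (illustration only).** Assume no true covering effect and a shift of b mm in mean width from arm-dependent filling. The chance of p<0.05 is P(|T| > t*), where T is noncentral t with noncentrality b/SE and t* is the two-sided 5% critical value (2.074 with 22 df, 2.101 with 18 df).

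| Assumed b (mm) | Share of 2.5 mm | b/SE, 12 per arm | False p<0.05, 12 per arm | False p<0.05, 10 per arm |
|---|---|---|---|---|
| 0 | 0% | 0 | 5.0% | 5.0% |
| 0.25 | 10% | 0.38 | 6.6% | 6.3% |
| 0.5 | 20% | 0.77 | 11.3% | 10.2% |
| 1.0 | 40% | 1.53 | 31.0% | 26.3% |

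For scale, the smallest observed difference that reaches p<0.05 is 2.074 × 0.653 = 1.35 mm with 12 per arm and 2.101 × 0.716 = 1.50 mm with 10.

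The values of b are assumptions. The documents contain nothing that links the amount of graft to ridge width among filled sockets. The legend of Figure 1 (section 1.4.1) says only that grafting reduces horizontal contraction compared with not grafting.

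**The case against.** The strongest reply is that the graft rule is the same in both arms and has a stated target. An amount that follows socket size is a way of standardising the fill. Socket size is fixed before treatment, so randomisation balances it on average; with 12 per arm some chance imbalance remains, but that is not bias. This stands. A reader might infer from the wording that the surgeon sets the amount freely; the shared target does not support that. Only filling that depends on the arm would bias the comparison.

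A reader might also infer that, because one covering is a plug and the other a matrix, a surgeon would leave a different fill beneath each. The documents do not say so. Section 5.3 uses both products to cover the grafted socket and gives no difference in seating or fill. Likewise, separate paragraphs for the two arms are an ordinary way to write a protocol and do not show that the arm is already known.

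The choice of rehydration fluid ("The bone substitute material will be rehydrated with subject's blood or sterile saline solution") is identical in both arms, and no mechanism is given by which it would differ between them, so nothing here rests on it.

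Finally, Visit 2 is written as narrative and the case report form is not among the documents, so the amount may in fact be collected. That is fair: the gap is in the plan as written. The illustration is also generic, since any bias of that size from any cause would give the same percentages, and at 0.25 mm the effect is small.

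What the reply does not remove is that the order of reveal and grafting is open, and that identical wording does not guarantee identical execution by someone who may know the arm.

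**Conclusion.** The point holds as a preventable risk of performance bias. The plan allows the surgeon to know the arm during the step both arms share, and as written offers no way to see whether that step was performed alike. The documents do not show that differential filling would occur, in which direction, or by how much.

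The illustrative range is a false-positive chance of about 7%, 11% or 31% instead of 5%, for assumed biases of 0.25, 0.5 or 1.0 mm. It rests on SD 1.6 mm, 12 per arm and no true covering effect, and it shows sensitivity, not expected size. The case for acting is that the change costs very little and closes this route to bias, not that a large bias has been established.

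**What to change.** In sections 3.2 and 5.3 (Visit 2), state that the envelope is opened only after the extraction and the buccal-plate check are complete and the graft is seated, immediately before the covering is placed. Align section 4.4, so that the number identifying the arm is not issued earlier. Placing the reveal after the buccal-plate check also means that subjects excluded at that check leave before their arm is known.

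Record the amount of graft used on the case report form, for example units or mg opened and placed, and add a table of it by arm to section 7.0.

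The cost is a few sentences of protocol text, a form entry and one table. Both coverings must be at hand, and the envelope is opened during surgery. If mg placed is recorded, part-used material may need weighing; counting units avoids this. No graft amount, fill height or rehydration fluid is proposed; those remain for the investigators.

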5.4 VISIT 3 (DAY 7 +/- 2 DAYS)

Visit 3 may occur within 7 days of visit 2 (+/-2 days). The following procedures will be performed:

- Study personnel will record changes in medical history and concomitant medications since the previous visit and ask continuance criteria questions.
- Participant vital signs (blood pressure and pulse) will be recorded.
- Two (2) gingival crevicular fluid (GCF) samples will be collected from the surgical site for archiving and later regenerative and inflammatory biomarker analysis. The GCF will be collected from the interproximal site of the surgical site without disturbing the healing.
- 3Shape Trios scanning will be completed for later volumetric analysis.
- The participant will be re-instructed to defer oral hygiene measures in the surgical site.
- Adverse events will be monitored and recorded as necessary

5.5 VISIT 4 (DAY 14 +/- 2 DAYS)

Visit 4 may occur within 7 days of visit 3 (+/-2 days). The following procedures will be performed:

- Study personnel will record changes in medical history and concomitant medications since the previous visit and ask continuance criteria questions.
- Participant vital signs (blood pressure and pulse) will be recorded.
- Two (2) GCF samples will be collected from the surgical site for archiving and later regenerative and inflammatory biomarker analysis. The GCF will be collected from the interproximal site of the surgical site without disturbing the healing.
- 3Shape Trios scanning will be completed for later volumetric analysis.
- Sutures will be removed if still present.
- The participant will be instructed to resume oral hygiene measures in the surgical site.
- Adverse events will be monitored and recorded as necessary

5.6 VISIT 5 (DAY 28 +/- 2 DAYS)

Visit 5 may occur within 14 days of visit 4 (+/-2 days). The following procedures will be performed:

- Study personnel will record changes in medical history and concomitant medications since the previous visit and ask continuance criteria questions.
- Participant vital signs (blood pressure and pulse) will be recorded.

- Two (2) GCF samples will be collected from the surgical site for archiving and later regenerative and inflammatory biomarker analysis. The GCF will be collected from the interproximal site of the surgical site without disturbing the healing.
- 3Shape Trios scanning will be completed for later volumetric analysis.
- The participant will be instructed to continue oral hygiene measures in the surgical site.
- Adverse events will be monitored and recorded as necessary

5.7 VISIT 6 (MONTH 3 +/- 7 DAYS)

Visit 6 may occur within 3 months of visit 2 (+/-7days). The following procedures will be performed:

- Study personnel will record changes in medical history and concomitant medications since the previous visit and ask continuance criteria questions.
- Participant vital signs (blood pressure and pulse) will be recorded.
- 3Shape Trios scanning will be completed for later volumetric analysis.
- Adverse events will be monitored and recorded as necessary

5.8 VISIT 7 (MONTH 6 +/- 7 DAYS)

Visit 7 may occur within 6 months of visit 2 (+/-7days). The following procedures will be performed:

- Study personnel will record changes in medical history and concomitant medications since the previous visit and ask continuance criteria questions.
- Participant vital signs (blood pressure and pulse) will be recorded.
- Standardized cone beam computed tomography (CBCT) will be taken for implant surgical planning.
- 3Shape Trios scanning will be completed for later volumetric analysis.
- Adverse events will be monitored and recorded as necessary

5.9 VISIT 8 (IMPLANT PLACEMENT +/- 7 DAYS)

Visit 8 may occur within 2 weeks of visit 7 (+/-7days). The following procedures will be performed:

- Study personnel will record changes in medical history and concomitant medications since the previous visit and ask continuance criteria questions.
- Participant vital signs (blood pressure and pulse) will be recorded.

- The surgeon will prepare the osteotomy sequential drills as dictated by the Straumann surgical kit and place a bone level, threaded titanium alloy implant with an internal connection using a surgical guide. Implants will be placed approximately 3-4mm below the free gingival margin or 2-3mm below the cemento-enamel junction of adjacent teeth. The implant insertion torque will be recorded at implant placement. A healing abutment will be placed for proper soft tissue healing.
- Biopsy collection of gingival and bone tissues. Biopsy collection will be done during the dental implant surgery when the surgeon removes discarded tissues over the implant site using a punch or a blade. Bone biopsy will be collected with a 2x5mm trephine bur at the site planned for implant placement.
- As part of standard operating procedure, intra-operative periapical radiographs (PA) will be taken after implant placement to verify implant placement.
- 3Shape Trios scanning will be completed for later volumetric analysis.
- Patients will be given prescriptions for postoperative medications as stated in Table 1. Patient will assume all costs for prescription medications.
- Adverse events will be monitored and recorded as necessary

5.10 VISIT 9 (POST-OP)

Visit 9 may occur 2 weeks after visit 9 (+/-2days). The following procedures will be performed:

- Study personnel will record changes in medical history and concomitant medications since the previous visit and ask continuance criteria questions.
- Participant vital signs (blood pressure and pulse) will be recorded.
- 3Shape Trios scanning will be completed for volumetric analysis.
- The participant will be instructed to resume oral hygiene measures in the surgical site.
- Adverse events will be monitored and recorded as necessary.

6.0 STUDY PROCEDURES AND EVALUATIONS

6.0 STUDY OUTCOMES

The primary outcome examined in this study will be the radiographic and soft tissue volume results following socket graft + use of collagen dressing or 3D-collagen matrix.

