7.0 STATISTICAL ANALYSIS

Descriptive statistics (means and standard deviations for continuous variables and frequencies for categorical variables) will be produced for vital signs, demographic characteristics, medical history and clinical variables, both overall, and for each of the two groups of study participants. Summaries of clinical variables will be presented at baseline and at study exit. Adverse events (including onset, duration, treatment, outcome and suspected causality) and reasons for withdrawals will be listed and summarized.

A power analysis was performed using a statistical power calculator (SAS Power Procedure, Cary, NC). This study will have a sample size of 24 subjects, 12 in each of the two groups. We will have at least 90% power (with a Type I error rate of 5%) to detect a difference of 2.5mm in the horizontal ridge width measured at 3mm below the most coronal aspect of the crest, assuming a standard deviation of 1.6mm, as determined by a previous study (Jung, Philipp et al. 2013). This power calculation takes into account the estimated 10% of subjects drop out. A “p” value of less than 0.05 will be considered statistically significant.

For soft tissue analysis, the primary outcome was the within-participant difference between the linear and volume changes at the test and control groups. These differences were measured in each participant prior to surgery, as well as 3 and 6 months after surgery, leading to a series of three longitudinal differences for each participant. For each group, the differences at all three time points were analyzed simultaneously using a linear mixed model (LMM), in which the actual linear and volume measures were modeled as a function of time (categorical), treatment group, and the interaction of time and treatment, while accounting for the repeated measures on each participant with a random participant effect. Given that both time and treatment are categorical, our approach was a generalized version of repeated measures ANOVA, as our LMM allowed for differing variability in linear and volume measures at each time point. Within each LMM, we also tested for a difference between the two treatment groups with respect to the overall time pattern in linear and volume measures. Due to the exploratory nature of the analysis, no Bonferroni correction for multiple testing was applied. Statistical significance was defined as a p -value < 0.05 .

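### Ridge width at 3 mm carries the only stated 5% error and 90% power but is never labelled primary, and no rule links it to the soft-tissue volume that shares the primary outcome

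*Combined protocol and SAP*

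**What the plan says.** **Primary outcome.** Section 6.0 (Study Outcomes) states: "The primary outcome examined in this study will be the radiographic and soft tissue volume results". It gives no variable and no combining rule.

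**Soft tissue.** The soft-tissue paragraph of Section 7.0 gives a second wording: "For soft tissue analysis, the primary outcome was the within-participant difference between the linear and volume changes". This adds a linear outcome that Section 6.0 does not mention. The same paragraph continues: "Due to the exploratory nature of the analysis, no Bonferroni correction for multiple testing was applied". It also reports that the model "tested for a difference between the two treatment groups with respect to the overall time pattern in linear and volume measures". The model uses three times (before surgery, 3 months, 6 months), whereas Section 6.6 lists six scan times.

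**Hard tissue.** The last paragraph of Section 7.0 says a two-sided equal-variance t-test "was performed comparing the two groups for each of the linear measurements as well as for the volumetric analysis", with significance at p < 0.05. Section 6.5 lists eight linear measures: buccal plate thickness at three levels, height at two aspects and ridge width at three levels.

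**Sample size.** The power statement in Section 7.0 concerns one variable. It claims at least 90% power at 5% type I error to "detect a difference of 2.5mm in the horizontal ridge width measured at 3mm below the most coronal aspect of the crest", with SD 1.6 mm and 12 per group. It adds: "This power calculation takes into account the estimated 10% of subjects drop out". Section 4.4 says: "Participants who do not complete the study will be replaced until 24 participants have completed the study".

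**Time point.** Aims 1 and 2 (Section 2.0) both run from baseline to month 6, and Section 6.5 fixes the CBCT comparison at the same two times.

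**The concern.** A primary outcome has to identify the result on which the trial will be judged. Here the general statement joins two domains, the soft-tissue paragraph describes one of them differently, and the sample size rests on a variable that neither statement names. Several readings are therefore open: HW-3 decides; any radiographic result decides; either domain decides; both must succeed. Each has a different error rate and a different power.

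Until one reading is fixed, a significant result on any of several measures could be reported as the primary finding without contradicting Section 6.0. A null result on HW-3 could likewise be set aside in favour of another measure. Labelling the soft-tissue analysis both primary and exploratory makes this worse, because the exploratory label is the reason given for applying no correction to an outcome that is also called primary.

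**Working it through.** **1. Reproduce the plan's figure.** Inputs from Section 7.0: difference 2.5 mm, SD 1.6 mm, two-sided 0.05, 12 per arm, 10% dropout. For the equal-variance t-test with n per arm, the noncentrality is 2.5 / (1.6 × √(2/n)) on 2n − 2 degrees of freedom.

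| n per arm | Standard error (mm) | Noncentrality | Critical t | Power |
|---|---|---|---|---|
| 10 | 0.7155 | 3.494 | 2.101 | 91.0% |
| 11 | 0.6822 | 3.664 | 2.086 | 93.6% |
| 12 | 0.6532 | 3.827 | 2.074 | 95.5% |

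Ten per arm is the smallest number that reaches 90%. Allowing for dropout, 10 / 0.90 = 11.1, which rounds up to 12 per arm, or 24. The plan's figure reproduces. With replacement under Section 4.4 the relevant row is 12. Without it, 12 × 0.90 = 10.8, or about 11. Section 7.0 does not say whether 1.6 mm is the SD of the change or of the 6-month value; these powers apply to the change only if it is the former.

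**2. Count the hard-tissue tests.** 3 + 2 + 3 = 8 linear measures, plus 1 volumetric analysis, makes 9.

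**3. False-positive chance if any one significant result counts.** No section states this rule. For k independent tests the chance is 1 − 0.95^k. The correlated columns are simulations with 12 per arm, equally correlated normal outcomes and t-tests at 0.05. A t-test stands in for the soft-tissue model. The documents give no correlations, so these are assumed.

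| Tests that count | Independent | 0.7 | 0.9 | 0.95 |
|---|---|---|---|---|
| One radiographic, one soft-tissue (k = 2) | 9.8% | 8.5% | 7.2% | 6.5% |
| All hard-tissue tests (k = 9) | 37.0% | 21.1% | 12.8% | 10.1% |

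**4. If both domains must succeed.** Type I error stays at or below 5%. Joint power cannot exceed the HW-3 power and depends on a soft-tissue test for which the documents give no effect size or SD. For illustration, with 12 per arm and independent tests, an assumed soft-tissue power of 80% gives 0.955 × 0.80 = 76%, and 90% gives 0.955 × 0.90 = 86%. Joint power of 90% would need soft-tissue power of 0.90 / 0.955 = 94%.

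**5. HW-3 power under a tighter threshold** (same formula, 12 and 11 per arm): at 0.025, 91.3% and 88.3%; at 0.05/9, 76.3% and 70.4%.

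**The case against.** The strongest defence is that HW-3 is a radiographic result, so it lies inside the declared primary outcome. It is the only variable with an effect size, SD, error rate and power, and Section 7.0 gives its test, sidedness and threshold. A reader could reasonably infer that it is the intended primary. It stands that HW-3 has valid error control and adequate power of its own, so it would be wrong to conclude that the plan has no error rate or power for any primary result. What does not stand is the inference that HW-3 alone is primary: Sections 6.0 and 7.0 both give soft tissue that status.

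Four further points have weight.

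- **Time point.** A reader of Section 6.0 alone might infer that no time point is fixed. Sections 2.0 and 6.5 settle the radiographic one. Only the soft-tissue time point is open, and only in the analysis.
- **Two primaries.** Two primary outcomes are legitimate, and requiring both causes no inflation. The gap is the missing rule, not the number of outcomes.
- **Size of the inflation.** A reader might take 37% as the trial's error rate. That needs an any-one-counts rule that no section states, a reading of radiographic results as every CBCT measure, and independence. Independence is implausible for widths and thicknesses taken on the same central section.
- **Disclosure.** The lack of correction is openly stated, but only for soft tissue. The hard-tissue paragraph has no exploratory label and speaks of testing a working hypothesis.

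**Conclusion.** The point holds as a missing label, a missing rule and an internal contradiction. The sample-size arithmetic is sound and HW-3's own test is valid. The stated 5% and 90% nevertheless do not cover the primary outcome as Section 6.0 words it.

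The consequence depends on the rule eventually adopted. Letting either one radiographic or one soft-tissue test suffice would give a false-positive chance of about 6.5% to 9.8%, for assumed correlations from 0.95 down to 0. Letting any of nine hard-tissue tests suffice would give about 10% to 37%, with the independent figure an unlikely upper end. Requiring both domains would leave the error rate intact and the power not established.

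The analysis paragraphs are in the past tense, and a reader might infer that outcome data had already been examined. The documents do not establish that. The wording is a reason to ask, because a primary outcome chosen after seeing data would not be prespecified.

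This should be settled before any result is called primary.

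**What to change.** **Preferred.** In Sections 6.0 and 7.0, name the between-group difference in change in HW-3 from baseline to month 6 as the primary outcome, tested at two-sided 0.05. Label the other hard-tissue outcomes and all soft-tissue outcomes secondary or exploratory, reported with estimates and 95% intervals. State that 1.6 mm is the SD of the change, or give the SD that is.

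**Alternative.** If soft-tissue volume stays primary, name one variable and one time point, and state one rule:

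- fixed order with HW-3 first, which leaves HW-3 power as it is but allows a soft-tissue claim only if HW-3 succeeds;
- both required, which needs a soft-tissue effect size and SD before power can be stated;
- 0.025 for each, which gives HW-3 power of 91.3% with 12 per arm or 88.3% with 11.

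If percent volume change is chosen, in line with Section 6.6, the mixed model in Section 7.0 must be changed to match, because it now models the actual measures.

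**In either case.** Remove the conflict between primary and exploratory in the soft-tissue paragraph. Date the change and state whether outcome data had been seen.

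**Cost.** The preferred fix is a change of wording, with N = 24 unchanged. The sponsor gives up the right to call an isolated p < 0.05 on another measure a primary result. If data have been seen, rewording cannot restore prespecification, and the choice must be disclosed as made afterwards.
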